## E. Assessments

Participants will undergo a series of assessments for initial baseline measurements and post-intervention measurements (Table 2). Both baseline and post-intervention evaluations will include a questionnaire, glucose tolerance, lower extremity strength testing (knee flexor), and upper extremity strength testing (grip strength). During the intervention phase, serum calcium and phosphorus levels will be monitored at every two weeks.

**Questionnaire:** The NIH-funded Patient-Reported Outcomes Measurement Information System Global-10 (PROMIS 10) is a brief, 10-question, multiple-choice survey that approximates a person's perceived physical and mental health (Hays et al. 2009). The questionnaire will be delivered as a written survey or in electronic format on a handheld tablet at the consent and screening visit as well as at the final visit for post-intervention assessments.

**Glucose Tolerance Test (GTT):** After an overnight fast, subjects will present to the Clinical Research and Trials Unit (CRTU). The subjects will ingest a drink containing 75g glucose. Venous blood will be obtained for measurement of glucose, insulin, and C-peptide concentrations over a 120 min period at 0, 10, 20, 30, 60, 90 and 120 minutes (Dalla Man et al. 2005; Sathananthan et al. 2012). All blood will be immediately placed on ice, centrifuged at 4°C, separated, and stored at -80°C until assay. Glucose will be measured using a Yellow Springs glucose analyzer, C-Peptide will be measured by ELISA assay using EMD Millipore (Billerica, MA) reagents, and insulin will be measured using a chemiluminescence assay with reagents obtained from Beckman (Chaska, MN). At the time of study, glucose values at 0 and 120 minutes will be used to categorize glucose tolerance status and exclude subjects with T2DM. Data obtained from GTT will provide fasting, peak, and nadir insulin concentrations. Additional calculations will be used to determine area above basal (AAB) or area under the curve (AUC) during the postprandial period using the trapezoidal rule as previously described (Vella et al. 2007). Insulin action ( $S_i$ ) and  $\beta$ -Cell responsivity indices ( $\phi$ ) will be calculated (Cobelli et al. 2014) from the plasma glucose, insulin and C-peptide concentrations observed during the experiments using the appropriate minimal model (Breda et al. 2001), incorporating age-associated changes in C-peptide kinetics (Cauter et al. 1992). The disposition index (DI) will be calculated as  $DI = \phi \cdot S_i$ , which determines if  $\beta$ -cell function is appropriate for the prevailing insulin action.

**Lower Extremity Strength Test:** Participants will undergo measurements at the Motion Analysis Laboratory. Dominant knee flexor musculature strength will be assessed via a computerized multi-joint testing system (Humac Norm System; CSMi Medical Solutions Stoughton, MA). Subjects will be positioned and stabilized on the testing apparatus using standardized protocols. The axis of the knee joint will be aligned with the center of rotation of the dynamometer arm and the lower leg will be strapped to the lever arm just proximal to the angle. Participants will be buckled in at the waist, shoulders and the distal part of the thigh. Peak torque will be assessed at a knee angle of 60° flexion. Participants will be verbally encouraged to perform at their maximum. Torque generated by the subject in an isometric contraction will be measured and recorded. Three isometric strength testing repetitions will be performed for each muscle group. Each isometric muscle contraction will be held for 5s and a 30s rest period will be observed between contractions. The largest value from three trials will be used.

Upper Extremity Strength Test: Isometric handgrip strength will be measured in the Motion Analysis Laboratory. Dominant hand grip strength will be tested using a custom designed digital grip dynamometer (NK Biotechnical Engineering Co., Minneapolis, MN). The measurements will be performed with participants sitting upright, feet flat on the floor, elbow flexed to 90°, and forearm in neutral position. Standardized verbal encouragement will be given for each contraction. Three maximal repetitions (30s rest between attempts) will be recorded. The largest value from three trials will be used.

Table 2: Timeline of the study

Consent, Screening, and Baseline Assessments (complete within 5 days)	
Day 1	Consent and Screening Completion of the PROMIS 10 Questionnaire Food Frequency Questionnaire Nutrition Consult with Dietitian Urinalysis (women only) 
 
• HCG
 
 Fasting Blood Draw 
 
• Basic Metabolic Panel, ALT, AST, BILIT, TSH, CBC, APT, PT, GLUCF, PTH, CDHVD (1,25(OH)2D3, 25(OH)D3), calcium, and phosphorus
 

Day 2	Glucose Tolerance Test 
 
• Glucose, insulin, glucagon and C-peptide, at fasting and at 10, 20, 30, 60, 90 and 120 minutes following oral glucose bolus
 
 Knee Flexor Strength Test Grip Strength Test Physical Exam with Physician Begin Intervention with 1,25(OH)2D3 or Placebo
Intervention	
Week 2	Blood Draw: calcium and phosphorus
Week 4	Blood Draw: calcium and phosphorus
Week 6	Blood Draw: calcium and phosphorus
Week 8	Begin Post-Intervention Assessments
Post-Intervention Assessments (complete within 2 days of taking last tablet )	
Day 1	Fasting Blood Draw 
 
• CDHVD (1,25(OH)2D3), calcium, and phosphorus
 
 Glucose Tolerance Test 
 
• Glucose, insulin, glucagon and C-peptide, at fasting and at 10, 20, 30, 60, 90 and 120 minutes following oral glucose bolus
 
 Knee Flexor Strength Test Grip Strength Test Completion of PROMIS 10 Questionnaire

## F. Statistics and Analyses

Power calculations for determining sample sizes were performed in JMP Pro 14 by using previously published variances on DI and  $\phi$  that describe beta cell function in pre-diabetic persons (Sathananthan et al. 2012) (Table 3).

Table 3: Power calculations for determining sample size

Parameter	Expected Outcome (mean $\pm$ sd)	Total Sample Size
DI	$1920 \pm 321$ ( $10^{-14}$ dl/kg/min $^2$ per pmol/l)	28
$\phi$	$63.8 \pm 7.5$ ( $10^{-9}$ min $^{-1}$ )	15
		47

\* Total N to detect a 20% difference with 85% power between two groups of N/2.

Analysis: Data will be analyzed as a repeated measures analysis of variance (ANOVA) with the independent variable as 1,25(OH) $_2$ D $_3$  or placebo and the dependent variable as assessments made before and after intervention. The main effect will be an analysis of the study groups pooled across gender and hormonal status to compare intervention with placebo. Additional co-variables to be considered in the analyses will be sex and menopausal stage per study group affiliation, as well as age, race, and others as post-hoc analyses.

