### Human Subjects

#### Risks to the subjects

Human Subjects Involvement and Characteristics: All protocols and all techniques to be used will be approved by the Mayo Clinic Institutional Review Board (IRB) prior to initiation of any studies. Subject characteristics and inclusion/exclusion criteria have been clearly specified above. Our plan is to complete the study on 50 participants with 25 in each group. We are anticipating a target accrual of 75 subjects to account for anticipated dropout in order to have 50 participants complete the study.

Sources of Materials. Samples of blood and urine obtained during the study will be used exclusively for research purposes. No use will be made of pre-existing specimens.

Urine: Urine samples will be collected from women for pregnancy testing.

Blood: One blood draw will occur during the screening visit (approximately 15 mL). A glucose tolerance test will be performed at baseline that will include seven blood draws (approximately 1 mL of blood from each draw) periodically over the course of 2 hours. Every 2 weeks during the intervention, a small sample of blood (1 mL) will be collected to monitor calcium and phosphorus levels. At completion of 8 weeks of intervention, another GTT will be performed and 5 mL of blood will be collected for post-intervention analysis. This analysis will include calcium, phosphorus, 25(OH)D $_3$ , 25(OH)D $_2$ , 1,25(OH) $_2$ D $_3$ , and 1,25(OH) $_2$ D $_2$ . All specimens will be processed internally and stored in the study team laboratory.

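### Does the unlabelled total of 47 in Table 3 leave the planned 50 completers without a basis?

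*Combined protocol and SAP*

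**What the plan says.** Section F of the combined protocol and SAP introduces the sample size in one sentence: "Power calculations for determining sample sizes were performed in JMP Pro 14 by using previously published variances on DI and" φ, with the variances taken from a cited study of insulin secretion and action. Table 3 then gives:

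| Parameter | Mean ± SD | Total N |
|---|---|---|
| DI | 1920 ± 321 | 28 |
| φ | 63.8 ± 7.5 | 15 |
| (none visible) | (none visible) | 47 |

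The footnote reads "Total N to detect a 20% difference with 85% power between two groups of N/2". Neither alpha nor sidedness is stated. The planned analysis in the same section is a repeated measures ANOVA of the assessments before and after intervention.

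The enrolment target stands elsewhere, under Human Subjects, Risks to the subjects: "Our plan is to complete the study on 50 participants with 25 in each group". The next sentence adds: "We are anticipating a target accrual of 75 subjects to account for anticipated dropout in order to have 50 participants complete the study". Neither sentence refers to Table 3.

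**The concern.** A reader who tries to trace 50 back to a calculation cannot do so. The introducing sentence names two parameters, and the larger of their requirements is 28. The table then shows 47, which is neither the larger requirement nor the sum of the two, and the target is 50. No sentence joins these numbers.

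If the 47 came from a wrong calculation, or if 50 had been derived from a mistaken figure, the only sample-size justification in the document would be unsound. There is also a question of interpretation: with 50 completers the trial has 85% power for a DI difference smaller than the footnote's 20%, so after a null result someone might ask which difference the trial was really sized to detect.

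**Working it through.** **Inputs.** From Table 3: DI mean 1920, SD 321; φ mean 63.8, SD 7.5. From the footnote: a 20% difference, 85% power, two equal groups. Assumed: two-sided alpha 0.05 and a two-sample t-test.

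**Standardised differences.**
- DI: 0.20 × 1920 = 384; d = 384/321 = 1.196.
- φ: 0.20 × 63.8 = 12.76; d = 12.76/7.5 = 1.701.

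**Formula.** With total N split equally, power is the probability that a noncentral t variable with N − 2 degrees of freedom and noncentrality λ = d√N/2 falls beyond the two-sided critical value.

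**Labelled rows.**
- DI, N = 28: λ = 1.196 × √28/2 = 3.165, critical t = 2.056, power 86.1%. At N = 27 power is 84.8%, so 28 is the smallest total that reaches 85%.
- φ, N = 15: λ = 1.701 × √15/2 = 3.295, critical t = 2.160, power 86.1%. At N = 14 power is 83.2%, so 15 is the smallest.

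Both stated figures reproduce exactly, which supports the assumed alpha. One-sided 0.05 would need 21.6 and 11.6, and two-sided 0.01 would need 39.9 and 21.6; neither matches the table.

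**Attempts at 47.**
- Larger requirement: 28. Sum: 28 + 15 = 43.
- Power at N = 47 for a 20% difference: 98.0% (DI) and 99.99% (φ), not 85%.
- A parameter that needs 47 under the footnote would have d of about 0.89, hence an SD of about 0.20/0.89 = 22% of its mean. DI has 321/1920 = 16.7% and φ has 7.5/63.8 = 11.8%.
- DI at a 15% difference: d = 288/321 = 0.897, requirement 46.6, rounded up to 47. This reaches 47 but departs from the footnote's 20%, so it is a possibility and not an explanation.

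**What 50 completers deliver.**
- Power for a 20% difference: DI, λ = 1.196 × √50/2 = 4.229, power 98.5%; φ, over 99.9%.
- Difference detectable with 85% power: d = 0.865, which is 0.865 × 321/1920 = 14.5% for DI and 0.865 × 7.5/63.8 = 10.2% for φ.
- Margin on the SD: power for 20% in DI stays at 85% or more until the SD reaches 384/0.865 = 444, or 444/321 = 1.38 times the cited value.

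**Accrual.** 75 accrued and 50 completing implies a loss of 25/75 = one third; 50/(1 − 1/3) = 75. The two enrolment figures agree with each other.

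**The case for a change.** The strongest case for a change is that Table 3 is the only sample-size justification in the document and part of it cannot be traced. The text names DI and φ alone, so a lost row label would not fully explain a third figure. Alpha is missing whatever the third row turns out to be, and so is the link from Table 3 to 50. Section G does not help, because its endpoints are completion of procedures and name no variable on which the trial was sized. The 15% route to 47 shows that the numbers are compatible with more than one design intention.

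All of that stands as a remark on reporting. It does not stand as a fault in the design. The 47 can be faulted only if it was meant to come from DI or φ, and nothing says so. A third entry in a column with one row per parameter reads more naturally as a third parameter. The document holds a hint of one: the reference list includes a 1995 paper on maximal sniff nasal inspiratory pressure that the body never cites, section B still speaks of diaphragm function, and section E contains no respiratory test. A measure dropped during editing would leave such traces, with 50 as 47 rounded up to 25 per group. This is inference, and that paper's SD is not available here to test it.

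The worry about a null result is also weaker than it looks. The footnote states the criterion, 20% at 85% power, and a null result would be read from its confidence interval, not from the label on a planning row.

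**Conclusion.** The observation is correct, but no change to the plan follows. Table 3 has an unlabelled figure, alpha is left unstated, and no sentence joins 50 to the table. These are clerical or reporting gaps. Both labelled rows are right at the customary two-sided 0.05, and a statistician recovers that alpha from them at once. The target of 50 exceeds 28, 15 and 47 alike, so whichever row it rests on, the footnote's criterion is met for DI and φ, at 98.5% and over 99.9% power for a 20% difference. Labelling or deleting the row would leave accrual, analysis and conclusions as they are.

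This rests on the assumed two-sided 0.05, on SDs from a cited study that could not be checked here, and on a two-sample t-test. It is not the power of the planned repeated measures ANOVA, which depends on a within-person correlation that the document does not give. Nor does it show that a 20% effect is realistic; it shows only that the stated criterion is more than met on the stated inputs.

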## Research Plan

### A. Specific Aim

The aim of this study is to assess the effects of 1,25(OH)2D3 on insulin secretion by the pancreas and glucose utilization by skeletal muscle as well as to determine the effects of 1,25(OH)2D3 on muscle strength in pre-diabetic subjects.

Hypothesis: 1,25(OH)2D3 will increase the rate of insulin secretion by pancreatic beta cells and improve glucose uptake in muscle, resulting in improved glucose homeostasis. Secondarily, 1,25(OH)2D3 will increase muscle strength.

Approach: This will be a double blind randomized control trial in pre-diabetic persons. Each participant will be randomly assigned to receive an oral tablet containing 0.25 µg 1,25(OH)2D3 or a placebo tablet for 8 weeks. Identical assessments will be performed both before and after the 8-week intervention period. These assessments will include the 2-hour glucose tolerance test (GTT) and muscle strength testing.

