## D. Design and Methods

### Study Design

We will compare insulin secretion and glucose uptake and muscle function before and after 8 weeks of treatment with 1,25(OH)2D3 or placebo in pre-diabetic participants. Men and women will be identified for recruitment to the study based on strict inclusion and exclusion criteria (Table 1 and *Enrollment Criteria*). After assignment to the study group, the participants will be randomly assigned on a first-come-first-serve basis to receive a daily oral tablet containing either 0.25 µg 1,25(OH)2D3 or placebo for 8 weeks. Before and after the intervention period, assessments will be made that will include a glucose tolerance test (GTT), knee flexor, and grip strength tests.

Table 1: Enrollment Groups

Group	Criteria
1	Men
2	Pre-menopausal Women

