#### G. Endpoints

Primary: Completion of final blood collection and GTT.

Secondary: Completion of PROMIS 10 Questionnaire.

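### The repeated-measures ANOVA leaves its efficacy term ambiguous and does not use the outcome's baseline as a covariate; a baseline-adjusted week-8 comparison is clearer and usually more precise at almost no cost

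*Combined protocol and SAP*

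**What the plan says.** Section F (Statistics and Analyses) specifies a repeated-measures ANOVA with 1,25(OH)2D3 or placebo as the independent variable and "the dependent variable as assessments made before and after intervention". The efficacy comparison is described in one sentence: "The main effect will be an analysis of the study groups pooled across gender and hormonal status to compare intervention with placebo". Sex and menopausal stage are listed as further co-variables, "as well as age, race, and others as post-hoc analyses". The text mentions no time factor, treatment-by-time interaction, change score or week-8 contrast, and it does not name the baseline value of the outcome as a covariate.

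The baseline exists for every outcome at issue. Section A (Specific Aim) says "Identical assessments will be performed both before and after the 8-week intervention period", and Table 2 schedules the glucose tolerance and strength tests both before and after treatment. Study Design frames the comparison the same way: "We will compare insulin secretion and glucose uptake and muscle function before and after 8 weeks of treatment".

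The footnote to Table 3 gives the sizing basis: "Total N to detect a 20% difference with 85% power between two groups of N/2". Human Subjects plans 50 completers, 25 per arm, from 75 accrued.

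**The concern.** Two things follow from the wording.

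First, with two arms and two visits, the treatment-by-time test is identical to a t-test on the change from baseline. That fixes the slope of week 8 on baseline at 1 instead of estimating it. When the true slope is below 1, the change score carries extra baseline noise, and the interval for the treatment effect is wider than the collected data allow.

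Second, in a repeated-measures ANOVA the term main effect has a technical meaning: the between-group difference averaged over visits. Baseline is measured before treatment, so randomised arms differ there only by chance. Averaging it in halves the expected estimate. The surrounding sentence suggests the authors meant the principal comparison pooled over men and women, but an analyst who runs the text literally would test the wrong quantity.

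The point concerns the model for whichever outcomes are tested. That Section G defines its primary endpoint by completion ("Primary: Completion of final blood collection and GTT") is a separate gap.

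**Working it through.** **Inputs from the documents.** DI mean 1920, SD 321, difference 20% (0.20 × 1920 = 384); φ mean 63.8, SD 7.5 (difference 12.76); power 85% (Section F, Table 3). 25 completers per arm (Human Subjects).

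**Assumed.** Two-sided α 0.05; rho 0, 0.3, 0.5, 0.7, 0.9; the same SD at both visits; normal outcomes. The documents give neither α nor rho.

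**Step 1: reproduce Table 3.** A two-sample t-test (noncentral t) with two-sided α 0.05 gives DI power of 86.1% at N = 28 and 84.7% at N = 27. For φ it gives 85.9% at N = 15 and 83.2% at N = 14. Both table entries (28 and 15) are reproduced. One-sided 0.05 gives 22 and 12 and does not fit. Table 3 therefore sizes a single-time-point comparison with no baseline term. At 25 per arm, that unadjusted week-8 test has 98.5% power for the 20% DI difference.

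**Step 2: variance factors**, in units of SD² × (1/25 + 1/25):
- treatment-by-time (change): 2(1 − rho), 48 df, estimates 384
- ANCOVA: (1 − rho²) × 47/46, 47 df, estimates 384. The factor 47/46 is the small-sample cost of estimating the slope.
- literal between-group term: (1 + rho)/2, 48 df, estimates 384/2 = 192

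Example at rho 0.5:
- The change/ANCOVA variance ratio is 1.0 / (0.75 × 1.0217) = 1.305.
- With d = 384/321 = 1.196, the change test has noncentrality 1.196/√0.08 = 4.23 and power 98.5%.
- The literal term has standardised effect (1.196/2)/√0.75 = 0.691, noncentrality 0.691/√0.08 = 2.44 and power 67%.

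**Step 3: results for DI, 25 per arm.** Half-widths are means over 20,000 simulated trials per rho; powers use the noncentral t.

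| rho | 0 | 0.3 | 0.5 | 0.7 | 0.9 |
|---|---|---|---|---|---|
| Change/ANCOVA variance ratio | 1.96 | 1.51 | 1.30 | 1.15 | 1.03 |
| 95% CI half-width, change | 257 | 215 | 182 | 141 | 81 |
| 95% CI half-width, ANCOVA | 184 | 175 | 159 | 131 | 80 |
| Power for 20%, change | 83% | 94% | 98.5% | >99% | >99% |
| Power for 20%, ANCOVA | 98% | 99% | >99% | >99% | >99% |
| Power for 20%, literal between-group term | 83% | 73% | 67% | 61% | 57% |

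The change test reaches 85% at rho of about 0.04. If the true DI difference were 15% (288, assumed), power would be 59/75/87/98/>99% for change and 87/90/94/99/>99% for ANCOVA. For φ, power for 20% is at least 85% under every reading.

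**Step 4: where ANCOVA is not best.** The unadjusted week-8 comparison is better when rho < √(1 − 46/47) = 0.146, by about 1% in width at most (182 against 184 at rho 0). The change score is better when 2/(1 + rho) < 47/46, that is rho > 92/47 − 1 = 0.957.

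**The case against.** The strongest reply is that this is a choice between two valid analyses and that nothing the plan promises is lost. Treatment-by-time power for the planned 20% DI difference is 94% at rho 0.3 and 98.5% at rho 0.5. It falls below 85% only if repeat measurements in the same person are almost uncorrelated. The size of the ANCOVA gain rests on a correlation that the documents do not give, and it shrinks to almost nothing at 0.9. The literal between-group reading is not the natural one, since Sections A and D frame the comparison as before against after. All of this stands, and it limits the point to precision and clarity.

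Three stronger readings are tempting but not supported:
- A reader might infer that the plan ignores baseline. It does not: baseline is one of the repeated outcomes, and treatment-by-time uses it with the slope fixed at 1. What is missing is baseline as a covariate.
- A reader might infer that no efficacy comparison is named. Section F does name one between intervention and placebo. The wording is ambiguous, not absent.
- A reader might infer that the trial needs more participants. At rho 0.5 a change analysis would need 50 × 1.305 = 65 completers, or 65.2 × 75/50 = 98 accrued, to match ANCOVA at 50. That is an equivalence in precision at one assumed rho. The change test with 50 completers already has 98.5% power there for the planned effect.

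What the reply does not answer is that the text still permits the half-size analysis, and that the sharper analysis needs no new data.

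**Conclusion.** The point holds as a minor one, best labelled a free improvement. The planned model, read sensibly, is valid and adequately powered for the stated DI difference unless rho is below about 0.04. It gives up precision that the collected baseline offers: from the table, the DI half-width would be 13% narrower under ANCOVA at rho 0.5 (159 against 182), 7% narrower at 0.7 (131 against 141) and about 1% narrower at 0.9 (80 against 81). Power becomes an issue only if the true effect is smaller than planned and rho is low to moderate, or if the between-group term is run literally. In the literal case DI power is below the stated 85% at every rho considered.

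These sizes rest on the assumed rho range, two-sided α 0.05 (which reproduces Table 3), an SD of 321 at both visits, and 25 completers per arm. They are for DI; the strength outcomes cannot be sized because the documents give no variance for them.

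**What to change.** In Section F, state that each week-8 outcome is analysed by ANCOVA with treatment and the baseline value of that outcome, and that the treatment coefficient with its 95% CI is the efficacy result. If the repeated-measures ANOVA is kept, name the time factor and state that treatment-by-time is the efficacy test. Either wording removes the half-size reading; only the first gains the precision.

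The cost is one sentence of text, one degree of freedom (48 to 47) and an assumed linear relation between baseline and week 8. No visit, sample or participant is added. The change does not address the planned loss of 25 of 75 participants (75 accrued for 50 completers), which needs its own provision.
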